4.2.3 Primary MRI Efficacy Endpoints

4.2.3.1 Proportion of patients free of atrial capture threshold increase of > 0.5V at 0.5ms from before and to one month after the MRI scan

4.2.3.2 Proportion of patients free of ventricular capture threshold increase of > 0.5V at 0.5ms from before to one-month after the MRI scan

The hypothesis is formally expressed as:

H_0 : Proportion of patients with threshold increase of $\leq 0.5V$ at 0.5ms from before to one month post MRI visit $\leq 90\%$

H_a : Proportion of patients with a threshold increase of $\leq 0.5V$ at 0.5ms from before to one month post MRI visit $> 90\%$

The desired outcome is to reject the null hypothesis. The null hypothesis is rejected at 2.5% significance level if the lower bound of the two-sided 95% confidence bound on the proportion of patients with a threshold increase of $\leq 0.5V$ at 0.5ms from before to one month post MRI visit is greater than 90%.

Sample Size

A success (Post-MRI scan Threshold – Pre-MRI scan Threshold) is defined as a patient who experiences an increase in threshold less than or equal to 0.5 volts at the 1 month post-MRI visit compared to their pre-MRI testing (MRI visit). In this case post MRI capture Threshold \leq pre MRI capture Threshold + 0.5 volts.

The % of Success (Post-MRI scan Threshold – Pre-MRI scan Threshold) is defined as the number of patients with successes divided by the analyzable patients.

In another manufacturer's study involving an MRI conditional pacemaker, the proportion of patients with an increase in threshold less than or equal to 0.5 volts at the 1 month post-MRI visit compared to their pre-MRI testing was 100%.¹⁹ Therefore, an assumption of 98% of successes (Post MRI scan-Pre-MRI scan threshold) in the atrium and ventricle is assumed in the sample size calculation.

A sample size of 93 patients provides 90% power to demonstrate a success rate greater than 90% for the atrial and ventricular endpoints, respectively, at the 2.5% significance level.

Analysis

The analysis will be conducted on the per-protocol population. The per-protocol population includes patients who meet the following criteria:

- Successfully implanted with the Accent MRI system
- Have MRI visit data
- Meet the MRI Conditions of Use
- Received an MRI scan
- Have 1 month post MRI visit data

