- Have a pacing threshold difference not exceeding 0.5 V at 0.5 ms between the two-month and MRI visit device pre-check, in cases where the MRI visit occurs approximately 9-12 weeks after the implant or system revision procedure since such short-term variability in pacing performance can be indicative of an abnormal lead/tissue interface that could confound analyses of MRI related effects.
- Have an atrial lead to be included in the '% success (change in atrial capture threshold)' endpoint analysis and/or a ventricular lead to be included in the '% success (change in ventricular capture threshold)' endpoint analysis
- Are not in AF at the time of atrial capture threshold measurements. Note: If atrial arrhythmias persist throughout the visit window for the MRI and/or 1 Month Post MRI visit, and no atrial capture threshold value can be obtained either at the MRI and/or 1 Month Post MRI visit, measured atrial capture threshold values from the next nearest timed visit may be substituted.

The proportion of patients not experiencing increases of 0.5V at 0.5ms for both atrial and ventricular capture thresholds will be calculated separately along with the associated 2.5% lower confidence bound. The lower bound for both of these proportions will be compared to the

OPC of 90%. The endpoints will be considered successful if the lower bound is greater than 90%.

Additional Analyses

A sensitivity analysis of the endpoint will be conducted using the ITT population, where both a worst and best case analysis will be performed. The worst case analysis will consist of treating all missing data as failures. The best case analysis will treat all missing data as successes.

4.2.3.3 Proportion of patients with atrial sensing amplitude decrease of $\leq 50\%$ and a sensing amplitude at 1-month post MRI visit of $\geq 1.5\text{mV}$

The hypothesis for the atrial sensing threshold is formally expressed as:

H₀: Proportion of patients with an atrial sensing amplitude decrease of $\leq 50\%$ and atrial sensing amplitude at 1-month post MRI visit of $>1.5\text{ mV} \leq 85\%$

H_a: Proportion of patients with an atrial sensing amplitude decrease of $\leq 50\%$ and atrial sensing amplitude at 1-month post MRI visit of $\geq 1.5\text{ mV} > 85\%$

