The analysis will be conducted on the per-protocol population. The per-protocol population includes patients who meet the following criteria:

- Successfully implanted with the Accent MRI™ system
- Have MRI visit data
- Meet the MRI Conditions of Use
- Received an MRI scan (if in the MRI group)
- Have 1-month post MRI visit data
- Have a pacing threshold difference not exceeding 0.5V between the two-month and three month post-implant (MRI scan pre-check), in cases where the MRI visit takes place approximately 9-12 weeks after an implant or system revision procedure since such short-term variability in pacing

performance can be indicative of an abnormal lead/tissue interface that could confound analyses of MRI related effects.

- Have a pre-MRI/pre-waiting period sensing amplitude greater than or equal to 5.0 mV in the ventricle or greater than or equal to 1.5 mV in the atrium.
- Have an atrial lead to be included in the ‘% success (change in atrial sensing amplitude)’ endpoint analysis and/or a ventricular lead to be included in the ‘% success (change in ventricular sensing amplitude)’ endpoint analysis
- Are not in AF at the time of atrial sensing amplitude measurements
- Have an intrinsic heart rate ≥ 30 beats per minute at the time of ventricular and/or atrial capture threshold measurements

The proportion of patients not experiencing an atrial sensing amplitude decrease of $\leq 50\%$ and atrial sensing amplitude at 1-month post MRI visit of >1.5 mV will be calculated. The associated 2.5% lower confidence bound will also be derived. This lower bound will be compared to the OPC of 85% and the endpoint will be considered successful if the lower bound is greater than 85%.

The proportion of patients not experiencing a ventricular sensing amplitude decrease of $\leq 50\%$ and ventricular sensing amplitude at 1-month post MRI visit of > 5 mV will be calculated. The associated 2.5% lower confidence bound will also be derived. This lower bound will be compared to the OPC of 87% and the endpoint will be considered successful if the lower bound is greater than 87%.

All individual primary efficacy endpoints must be successful (reject the null hypothesis at the $\alpha = 2.5\%$ level) for the efficacy endpoint to be successful.

Additional Analyses

The same additional analyses described above in section 4.2.3.1 and 4.2.3.2 will be completed for this endpoint if required.

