
* Note: RA lead measurements are not required if a single chamber device is implanted. RA capture and sensing thresholds are not required if a patient is in atrial fibrillation or atrial flutter. If the RA capture and sensing thresholds could not be obtained due to a patient's atrial fibrillation or flutter, and if the patient's atrial fibrillation or flutter is transient, for data analysis purposes, the pacing capture threshold and sensing threshold from the next study visit, if available, will be used.
 
RA/RV sensing measurements are not required if the patient's intrinsic rate has been established to be below 30 beats per minute. RV capture thresholds are not required if a high ventricular rate is present.
 
+Study site must verify that the MRI consent has been signed and patient meets criteria to undergo MRI scan
					

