4.4.6.6 MRI Visit

IMPORTANT NOTE: For patients participating in the MRI portion of the study, prior to the MRI visit, if the patient underwent a system revision that resulted in

- capping of the MRI lead(s),
- plugging of a port, or
- implant of a non-MRI lead or device, OR
- any combination above,

the patient is not eligible to undergo a study MRI Scan. Do not proceed with any of the tests listed for the MRI Visit. If not already done, discontinue the patient from the MRI component of the study. Refer to section 4.4.6.5 for further details.

Otherwise, follow the procedures outlined below for the MRI Visit.

Cardiac Medications and Pregnancy Testing

Document all cardiac medications. Administer a pregnancy test to all female patients of childbearing potential.

Pre-MRI Scan: Pacemaker Device Measurements

Evaluate the patient for adverse events. Perform a device interrogation, and obtain the following electrical measurements for the RA and/or RV leads.

- Manual **unipolar** capture threshold at a pulse width of 0.5 ms using the Decrement Threshold test method. Pace at least three cycles per step, and confirm at least three consecutive beats have capture before recording the capture threshold results.

- Manual **bipolar** capture threshold at a pulse width of 0.5 ms using the Decrement Threshold test method. Pace at least three cycles per step, and confirm at least three consecutive beats have capture before recording the capture threshold results.
- Bipolar sensing amplitude using the Incremental Test Method. Set the required sensed beats to at least 3 cycles per step. Confirm at least three consecutive beats are sensed before recording the sensing threshold results.
- Bipolar lead impedance

Note: RA lead measurements are not required if a single chamber device is implanted. RA capture and sensing thresholds are not required if a patient is in atrial fibrillation or atrial flutter. If the RA capture and sensing thresholds could not be obtained due to a patient's atrial fibrillation or flutter, and if the patient's atrial fibrillation or flutter is transient, for data analysis purposes, the pacing capture threshold and sensing threshold from the next study visit, if available, will be used.

RA/RV sensing measurements are not required if the patient's intrinsic rate is established to be below 30 beats per minute. RV capture thresholds are not required if a high ventricular rate is present.

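### The transient-AF substitution rule lets a post-scan visit supply the pre-scan baseline of the primary atrial capture endpoint

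*Combined protocol and SAP*

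**What the plan says.** Section 4.2.3 (4.2.3.1 and 4.2.3.2) counts a patient as a success if the capture threshold at the 1 Month Post MRI visit has risen by no more than 0.5 V, "compared to their pre-MRI testing (MRI visit"). The lower 95% bound on the success proportion must exceed 90%.

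Section 4.4.6.6, in the note to the pre-scan device measurements, says that "RA capture and sensing thresholds are not required if a patient is in atrial fibrillation or atrial flutter". If the arrhythmia is transient, "the pacing capture threshold and sensing threshold from the next study visit, if available, will be used". The note to Table 2 repeats this ("for data analysis purposes, the pacing capture threshold and sensing threshold from the next study visit, if available, will be used"), and so does section 4.4.6.7 for the 1 Month Post MRI visit. None of the three places says on which side of the scan the donor visit must lie.

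The per-protocol criteria for capture in section 4.2.3 contain another rule. If arrhythmia persists through the visit window and "no atrial capture threshold value can be obtained either at the MRI and/or 1 Month Post MRI visit", then "measured atrial capture threshold values from the next nearest timed visit may be substituted". For atrial sensing, the corresponding criterion is only "Are not in AF at the time of atrial sensing amplitude measurements", with no substitution.

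**The concern.** The endpoint asks what the scan did to the lead, so its baseline has to be measured before the scan. The note sits under the pre-scan measurements, is mandatory, and points to the next study visit. If the scan goes ahead on the day of the failed test, every later visit is post-scan.

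- **Donor is the 1 Month Post MRI visit.** The same reading is both baseline and outcome, and the change is zero whatever happened.
- **Donor is a 6- or 12-month lead-safety visit that falls in between.** The change is not forced to zero, but any rise already present by then is absorbed into the baseline.

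Atrial capture is a primary endpoint, and the plan requires every primary endpoint to succeed. The error runs toward passing. Because the plan holds two substitution rules, two analysts could also build different primary datasets from the same records.

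**Working it through.** **1. Does the text allow a scan without a pre-scan atrial value?** In section 4.4.6.6:

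- The stop-and-retest clause applies when required testing fails, but the atrial test is waived in AF.
- The condition for going on is that measurements were obtained per protocol, and the waiver is part of the protocol.
- The checklist and the system-check summary ask for stable capture thresholds. They do not say how to treat an atrial lead that cannot be tested that day.

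The per-protocol population in 4.2.3 must have been scanned, yet its AF note provides for patients with no atrial value at the MRI visit. The plan therefore foresees the case.

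**2. The two substitution rules side by side**

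| | Table 2 note, 4.4.6.6, 4.4.6.7 | 4.2.3 per-protocol note |
|---|---|---|
| Trigger | transient AF or flutter | arrhythmia persisting through the window |
| Donor | next study visit | next nearest timed visit |
| Force | mandatory | optional |
| Measures | capture and sensing | capture only |
| Post-scan donor barred as baseline? | no | no |

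Table 4 gives the MRI visit no closing date, so persistence through its window is not defined.

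**3. The plan's own figure.** Inputs from 4.2.3: p0 = 0.90, p1 = 0.98, one-sided 2.5%, power 90%.

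n = [(1.960·√(0.90·0.10) + 1.282·√(0.98·0.02)) / 0.08]² = 92.02, rounded up to 93, as stated. The sample size is sound; the fault lies in the data rule.

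**4. Pass limits.** The largest number of failures for which the exact lower 95% bound exceeds 90% is 3 of 93, 4 of 109, 10 of 182 and 25 of 363. A z-test with null variance gives the same limits. The sizes are:

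- 93, the planned number;
- 0.30 × 363 = 109, from the anticipated minimum atrial-lead share in 4.1;
- 0.50 × 363 = 182, from 400 RA leads among 800 patients in 4.2.1;
- 363, a ceiling with an atrial lead in every MRI-phase patient.

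The second and third assume that the MRI phase has the same atrial-lead share as the whole study.

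**5. Chance of passing when the true rate is 90%.** Let m patients take their baseline from the 1-month visit and so count as successes. Then P(pass) = P(Bin(n − m, 0.10) ≤ limit). The shares are assumptions.

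| n | none | 3% | 5% | 10% | 15% | first m above 2.5% |
|---|---|---|---|---|---|---|
| 93 | 1.3% | 1.7% (m=3) | 2.0% (5) | 2.6% (9) | 3.8% (14) | 9 (9.7%) |
| 109 | 1.3% | 1.6% (3) | 1.8% (5) | 2.7% (11) | 3.8% (16) | 10 (9.2%) |
| 182 | 2.2% | 2.9% (5) | 3.5% (9) | 5.5% (18) | 8.5% (27) | 3 (1.6%) |
| 363 | 2.5% | 3.8% (11) | 4.8% (18) | 8.9% (36) | 15.2% (54) | 1 (0.3%) |

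If the 1-month visit is the donor for only half of the substituted patients, the four shares give 1.5, 1.6, 2.0 and 2.3% at n = 93, and 2.6, 2.9, 3.5 and 4.5% at n = 182.

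**6. At the design rate of 98%, n = 93.** P(Bin(93, 0.02) ≤ 3) = 88.3%. With 5 substituted, P(Bin(88, 0.02) ≤ 3) = 90.0%.

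**The case against.** The strongest reply is that the harmful case needs a chain of events: an atrial lead, AF at the pre-scan test, AF that proves transient, a scan that proceeds anyway, no intervening visit as donor, and no later exclusion. Section 4.4.6.6 lets the schedule be revised after sponsor contact, and with no closing date a patient can return for a test before the scan. The per-protocol set also requires MRI visit data and compliance with the Conditions of Use. These points bear on how often the problem arises. They do not close the gap, because the atrial test is waived in AF, other MRI-visit data could satisfy the data criterion, and the documents do not spell out the Conditions of Use.

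The two rules can also be read as complementary, one for transient and one for persistent arrhythmia. That is a fair reading. It does not help, since neither bars a post-scan baseline.

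The stability criterion ("Have a pacing threshold difference not exceeding 0.5 V at 0.5 ms between the two-month and MRI visit device pre-check") is a real filter for scans at about 9-12 weeks. If the 1-month value stands in for the pre-check, a rise above 0.5 V since the 2-month visit leads to exclusion, not to a forced success. The step 5 table counts every such patient as a success and is therefore an upper end.

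The n = 363 row is a ceiling; the plan's own figures point to a share of roughly 30 to 50% with an atrial lead. The planned worst-case and best-case analyses help only in part, because the plan does not say whether a substituted value counts as missing.

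**Conclusion.** The concern holds. As written, the transient-AF rule allows a post-scan measurement to serve as the pre-scan baseline of a primary endpoint. Where the donor is the 1-month visit, failure is impossible.

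The size is uncertain because no AF frequency is given. Under the assumed shares, the chance of a false pass stays below the nominal 2.5% at the planned 93 patients until 9 are substituted, because the exact test there starts at 1.3%. At 182 patients it crosses 2.5% with 3 substituted. There is no effect where a retest is done before the scan or only pre-scan donors are used. The reason to act is that the rule gives the wrong baseline however many patients it touches.

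The figures concern atrial capture only. Atrial sensing is affected only if the visit notes override the sensing criterion in 4.2.3, and no figure is claimed for it.

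**What to change.** 1. State in 4.2.3, Table 2 and 4.4.6.6 that no measurement taken after the scan may serve as the pre-scan value. Limit next-visit substitution to the 1-month value, or to a repeat test still done before the scan.
2. Treat a patient with no admissible pre-scan atrial value as not evaluable in the primary analysis, and as missing in the planned worst-case and best-case analyses.
3. Decide in advance whether an earlier pre-scan study visit may be the donor in the primary analysis or only in a sensitivity analysis. For scans at about 9-12 weeks, a 2-month donor makes the stability criterion zero by construction; for later scans this does not arise.
4. Merge the capture and sensing criteria in 4.2.3 and the notes in Table 2, 4.4.6.6 and 4.4.6.7 into one rule. Reconcile the parts of 4.4.6.6 on whether a scan proceeds without an atrial value; no position is taken here on which way.
5. Report the number of substituted patients and the donor visit for each.

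The cost is wording plus a few non-evaluable atrial patients, and none where an earlier pre-scan donor is allowed and available. If 5, 10 or 15% are lost and not replaced, exact power at a true rate of 98%, P(Bin(n − m, 0.02) ≤ limit recomputed at n − m), goes from 88% to 90, 76 or 79% at n = 93, and from 93% to 94, 87 or 88% at n = 109. It stays above 99% at n = 182. The uneven steps come from whole-number pass limits: at n = 93 the limit drops from 3 failures to 2 once 9 patients are lost.

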4.4.6.8 Non-Study MRI Scan

A non-study MRI scan is defined as a scan occurring at any time following enrollment up to the completion of the study, excluding the MRI scan performed during the MRI Visit. Non-study MRI scans should be performed per each center's standard of care.

For non-study MRI scans performed at the study center, the same safety data collection and safety precautions outlined at the MRI visit should be followed. However, if procedures or data are not followed or collected as presented on the non-study MRI form during a non-study MRI scan, it will not be considered a protocol deviation.

MRI Scan Analysis

The MRI scan should be reviewed for obvious abnormalities by a radiologist, and reported to the patient's physician (per standard of care by the facility performing the MRI scan).

The following data should be collected, and reported to St. Jude Medical for non-study MRI scans:

- Date of scan
- Type of scan performed
- Documentation of any Adverse Events
- Device diagnostics, if available
- MRI Scan report, if available
- Fast Path Summary, if available

Data Submission

If the patient undergoes a non-study MRI scan at any time during the study, please complete and submit the forms listed below to St. Jude Medical. Upload device session records, if applicable and available, through the EDC study site portal. Device session records may also be sent to St. Jude Medical CRMD, Sylmar, CA.

- Non-study MRI Scan Form
- Adverse Event Form, if applicable
- Death, if applicable
- Withdrawal Form, if applicable

It is recommended that the following forms, device printouts and measurements be maintained at the site.

- MRI Safety Screening Form
- MRI Hazard Checklist
- FastPath Summary
- Test Results with Large Freezes, Include Battery & Leads
- Wrap-up Overview with full parameters

5.0 Protocol Deviations

Investigators are required to adhere to the investigational plan, signed Investigator's Agreement, applicable federal (national) or state/local, laws and regulations, and any conditions required by the IRB/MEC or applicable regulatory authorities.

A protocol deviation is used to describe situations in which the clinical protocol was not followed. All deviations from the investigational plan must be reported to St. Jude Medical per 21 CFR §812.150. In addition, all deviations must be reported to the reviewing IRB per the IRB's reporting requirements.

The investigator must notify St. Jude Medical and the reviewing IRB of any deviation from the investigational plan to protect the life or physical well-being of a patient in an emergency as soon as possible, but not later than 5 working days after the deviation has occurred, or no later than 5 working days after the investigator becomes aware of the deviation.

6.0 Adverse Events

A Clinical Events Committee (CEC) will review and adjudicate all Adverse Events. The CEC will base their final adjudication on the information provided on the case report forms, medical records, and their clinical knowledge and experience.

Adverse events (AEs) are any unfavorable clinical event which impacts, or has the potential to impact the health or safety of a patient caused by or associated with a study device or intervention. Adverse events will be classified as complications or observations.

Complications: Adverse events that require invasive intervention (e.g. lead dislodgment requiring repositioning).

Observations: Adverse events that can be managed without invasive intervention (e.g., oversensing or loss of pacing capture, which is remedied by reprogramming of the pacemaker).

Should an adverse event occur, complete an Adverse Event form and submit to St. Jude Medical. Report the adverse event to the IRB/MEC per the IRB/MEC policy. Any explanted devices or leads should be returned to St. Jude Medical for analysis.

Unavoidable AE: An unavoidable AE is defined as an adverse event related to the implant procedure or the MRI scan that is expected to occur for a projected duration in all patients. Unavoidable AEs are not reportable unless the condition worsens or continues beyond the time frame listed below. Unavoidable AEs, listed below, do not need to be reported if they are resolved within the time frame specified.

Table 6: Unavoidable AEs related to the Implant Procedure

Event	Time Frame post-Implant
Anesthesia related nausea/vomiting	<24 hours
Low-grade fever (<100 degree Fahrenheit fever or < 37.8 degree Celsius	< 48 hours
Pocket site/incision pain	< 72 hours
Mild to moderate bruising/ecchymosis at pocket site	< 72 hours
Sleep problems (insomnia)	< 72 hours
Back pain related to laying on the table	< 72 hours

Table 7: Unavoidable AEs related to the MRI Scan

Event	Time Frame post – MRI scan
Claustrophobia	During MRI scan
Mild diaphoresis	During and < 1 hour post MRI scan
Sensation of bodily warmth	During and < 1 hour post MRI scan
Hearing impairment	< 24 hours
Body stiffness related to immobility	< 48 hours

Definitions of AE relatedness:

Pacing system related: An AE that results from the presence or performance of the system under investigation.

Implant procedure related: An AE that occurs due to the implant procedure.

MRI scan related: An AE which is caused by the interaction between the investigational pacing system and the MRI system that occurs during the MRI scan and includes the time the patient is within the 5 Gauss line of the MRI system and up through the patient’s 1 month post MRI scan follow up visit. In addition, AE’s occurring due to the patient’s MRI programming will be considered MRI scan related.

Potential MRI System Adverse Events:

- Lead electrode heating and tissue damage resulting in loss of sensing or capture or both
- Lead heating resulting in thrombus formation or embolism
- Device heating resulting in tissue damage in the implant pocket or patient discomfort or both
- Induced currents on leads resulting in continuous capture, VT/VF, hemodynamic collapse, or all three
- Damage to the device or leads causing:

- the system to fail to detect or treat irregular heartbeats
- the system to treat the patient's condition incorrectly
- Damage to the functionality or mechanical integrity of the device resulting in the inability of the device to communicate with the programmer
- Movement or vibration of the device or leads
- Lead dislodgment
- Competitive pacing and potential for VT/VF induction due to ambulatory asynchronous pacing in MRI mode
- Pulmonary Embolism

Potential Pacing System Adverse Events:

- Air embolism
- Body rejection phenomena
- Cardiac tamponade or perforation
- Hematoma, bleeding hematoma, seroma
- Formation of fibrotic tissue; local tissue reaction
- Inability to interrogate or program due to programmer or device malfunction
- Infection/erosion
- Interruption of desired pulse generator function due to electrical interference either electromyogenic or electromagnetic
- Loss of capture or sensing due to lead dislodgement or reaction at the electrode/tissue interface
- Loss of desired pacing and/or sensing due to lead displacement, body reaction at electrode interface, or lead malfunction (fracture or damage to insulation)
- Lead malfunction due to conductor fracture or insulation degradation
- Loss of normal pacemaker function due to battery failure or component malfunction
- Pacemaker migration, pocket erosion
- Pectoral muscle stimulation
- Phrenic nerve or diaphragmatic stimulation
- Pneumothorax/hemothorax
- Endocarditis
- Excessive bleeding
- Induced atrial or ventricular arrhythmias
- Myocardial irritability
- Pericardial effusion
- Pericardial rub
- Pulmonary edema
- Rise in threshold and exit block
- Valve damage

Potential lead related adverse events

- Cardiac tamponade
- Diaphragmatic/phrenic nerve stimulation
- Embolism
- Excessive bleeding
- Induced ventricular ectopy
- Infection
- Loss of pacing and/or sensing due to dislodgement or mechanical malfunction of the pacing lead
- Thrombosis

Complications reported with direct subclavian venipuncture include pneumothorax, hemothorax, laceration of the subclavian artery, arteriovenous fistula, neural damage, thoracic duct injury, cannulation of other vessels, massive hemorrhage and rarely, death.

As defined in 21 CFR §812.3, **UNANTICIPATED ADVERSE DEVICE EFFECTS (UADE)** are defined as any serious adverse effect on health or safety or any life-threatening problem or death caused by, or associated with, a device, if that effect, problem, or death was not previously identified in nature, severity, or degree of incidence in the investigational plan or application (including a supplementary plan or application), or any other unanticipated serious problem associated with a device that relates to the rights, safety, or welfare of patients.

If an **UNANTICIPATED ADVERSE DEVICE EFFECT** occurs, the investigator must notify St. Jude Medical and the IRB/MEC immediately, but no later than 10 working days of the investigator's knowledge of the event, as required by 21 CFR §812.150. St. Jude Medical will take any steps necessary to investigate the event, and will be responsible for notifying FDA and all other participating IRBs/MECs and investigators.

Should St. Jude Medical determine, either through physician reports or in-house testing, that an unanticipated adverse event presents an unreasonable risk to participating patients, St. Jude Medical will suspend the clinical investigation and notify all participating investigators, IRBs/MECs and the FDA.

